#### **6.6.1.3. Adverse events leading to interruption of study treatment**

The eCRF does not allow for a clear separation between interruption of an infusion and delays of administration for a parenteral drug as both are recorded using the same term on the eCRF (“Drug interrupted”). IRRs will be excluded in the analysis of AEs leading to Drug Interruption in case they only led to an interruption of the infusion (ie, did not lead to a dose reduction or a dose delay).

As such, AEs leading to interruption will be defined as AEs identified in the AE eCRF page with an action taken with study treatment of ‘drug interrupted’ excluding:

- IRRs that occurred on the day of infusion with  $\geq 90\%$  of the planned dose given (ie, IRRs that did not lead to a dose reduction) and subsequent administration of study drug had no delay (as defined in Section 6.5.3.5). These IRRs will be considered as IRRs leading to interruption of infusion.
- IRRs occurring on the day after infusion and subsequent dose administration had no delay (as defined in Section 6.5.3.5).

The frequency (number and percentage) of patients with each of the following will be presented for TEAEs leading to interruption of each study drug by treatment arm:

- TEAEs leading to interruption of avelumab by SOC and PT;
- TEAEs leading to interruption of cisplatin by SOC and PT;
- TEAEs leading to interruption of IMRT by SOC and PT.

The listing of all AEs leading to interruption of study treatment will also be provided with the relevant information.

In addition, the frequency (number and percentage) of patients with each of the following will be presented for TEAEs leading to interruption of each study drug by treatment arm:

- TEAEs leading to both interruption and dose reduction of avelumab by SOC and PT;
- TEAEs leading to both interruption and dose reduction of cisplatin by SOC and PT;
- TEAEs leading to both interruption and dose reduction of IMRT by SOC and PT.

This summary will take into account PTs with both actions as defined in Section 6.6.1, eventhough the actions may be captured for different PT records (ie, different onset for the PT with action “drug interrupted” and the PT with action “dose reduced”).

#### **6.6.1.4. Adverse events leading to discontinuation of study treatment**

The frequency (number and percentage) of patients with each of the following will be presented for TEAEs leading to permanent discontinuation of each study drug and study treatment, by treatment arm:

- TEAEs leading to discontinuation of avelumab by SOC and PT;
- Related TEAEs leading to discontinuation of avelumab by SOC and PT;
- TEAEs leading to discontinuation of cisplatin by SOC and PT;
- Related TEAEs leading to discontinuation of cisplatin by SOC and PT;
- TEAEs leading to discontinuation of IMRT by SOC and PT;
- Related TEAEs leading to discontinuation of IMRT by SOC and PT;
- TEAEs leading to discontinuation of any study drug by SOC and PT (CRT Phase);
- Related TEAEs leading to discontinuation of any study drug by SOC and PT (CRT Phase);
- TEAEs leading to discontinuation of all study drugs by SOC and PT (CRT Phase);
- Related TEAEs leading to discontinuation of all study drugs by SOC and PT (CRT Phase).

The listing of all AEs leading to treatment discontinuation will also be provided with the relevant information.

In addition, the frequency (number and percentage) of patients with TEAEs leading to discontinuation of avelumab will be summarized by SOC and PT within each treatment arm and treatment phase.

#### **6.6.2. Deaths**

The frequency (number and percentage) of patients in the safety analysis set who died and who died within 30 days after last dose of study treatment as well as the reason for death, will be tabulated based on information from the ‘Notice of Death’ and ‘Survival Follow-Up’ eCRFs, by treatment arm, and by treatment arm and treatment phase.

- All deaths
- Deaths within 30 days after last dose of study treatment
- Reason for Death
  - Disease progression;

- Study treatment toxicity;
- AE not related to study treatment;
- Unknown;
- Other.

In addition, date and cause of death will be provided in individual patient data listing together with selected dosing information (study treatment received, date of first / last administration, dose) and will include the following information:

- AEs with fatal outcome (list preferred terms of AEs with outcome=Fatal, as well as AEs of Grade 5);
- Flag for death within 30 days of last dose of study treatment.

### **6.6.3. Serious adverse events**

The frequency (number and percentage) of patients with each of the following will be presented for treatment-emergent SAEs by treatment arm:

- SAEs by SOC and PT;
- Related SAEs by SOC and PT.

In addition, the frequency (number and percentage) of patients with SAEs will be summarized by SOC and PT within each treatment arm and treatment phase.

The listings of all SAEs will also be provided with the relevant information with a flag for SAEs with onset outside of the on-treatment period.

### **6.6.4. Other significant adverse events**

The frequency (number and percentage) of patients with each of the following will be presented for irAEs, by treatment arm:

- irAEs leading to death, by Cluster and PT;
- irAEs, by Cluster and PT;
- irAEs, Grade  $\geq 3$ , by Cluster and PT;
- irAEs leading to discontinuation of avelumab, by Cluster and PT;
- irAEs leading to discontinuation of cisplatin, by Cluster and PT;
- irAEs leading to discontinuation of IMRT, by Cluster and PT;
- irAEs leading to discontinuation of any study drug, by Cluster and PT (CRT Phase);
- irAEs leading to discontinuation of all study drugs, by Cluster and PT (CRT Phase);
- Serious irAEs, by Cluster and PT.

In addition, the frequency (number and percentage) of patients with each of the following will be presented for irAEs by treatment arm and treatment phase:

- irAEs, by Cluster;
- irAEs, Grade  $\geq 3$ , by Cluster;
- irAEs leading to death, by Cluster;
- irAEs leading to discontinuation of avelumab, by Cluster;
- Serious irAEs, by Cluster.

The listing of all irAEs will also be provided with the relevant information with a flag for irAEs with onset outside of the on-treatment period.

The frequency (number and percentage) of patients with each of the following will be presented for IRRs, by treatment arm:

- IRRs leading to death, by PT (separately for IRRs associated with avelumab, associated with cisplatin, associated with either avelumab or cisplatin);
- IRRs, by PT (separately for IRRs associated with avelumab, associated with cisplatin, associated with either avelumab or cisplatin);
- IRRs, Grade  $\geq 3$ , by PT (separately for IRRs associated with avelumab, associated with cisplatin, associated with either avelumab or cisplatin);
- IRRs leading to discontinuation of avelumab, by PT;
- IRRs leading to discontinuation of cisplatin, by PT;
- IRRs leading to discontinuation of any study drug, by PT (CRT Phase);
- IRRs leading to discontinuation of all study drugs, by PT (CRT Phase);
- Serious IRRs, by PT (separately for IRRs associated with avelumab, associated with cisplatin, associated with either avelumab or cisplatin);
- Time related to first onset of an IRR associated with avelumab (infusion 1, infusion 2, infusion 3, infusion 4 or later).

In addition, the frequency (number and percentage) of patients with each of the following will be presented for IRRs by treatment arm and treatment phase

- IRRs associated with avelumab, by PT
- IRRs associated with avelumab, Grade  $\geq 3$ , by PT
- IRRs associated with avelumab leading to death, by PT
- IRRs leading to discontinuation of avelumab, by PT;
- Serious IRRs associated with avelumab, by PT;
- Time related to first onset of an IRR associated with avelumab.

The listing of all IRRs will also be provided with the relevant information with a flag for IRRs with onset outside of the on-treatment period.

In addition, the following analyses will be presented for Tier-1 (irAEs and IRRs as defined in Appendix 1 and Appendix 2, respectively) and Tier-2 events separately. CIs for risk difference will be calculated based on the unconditional exact method by Santner and Snell (1980). No additional analyses will be presented for Tier-3 AEs.

- Frequency (number and percentage) of patients with each of the following by treatment arm and PT or Clustered Term:
  - Tier-2 AEs
  - Tier-2 AEs Grade  $\geq 3$
- Point estimate for risk difference and 95% CI for risk difference (experimental arm vs comparator arm) for each of the following by PT or Clustered Term:
  - irAEs
  - irAEs Grade  $\geq 3$
  - IRRs associated with avelumab
  - IRRs associated with avelumab, Grade  $\geq 3$
  - Tier-2 AEs
  - Tier-2 AEs Grade  $\geq 3$
- The CIs reported are not adjusted for multiplicity and should be used for screening purposes only. The 95% CIs are provided to help gauge the precision of the estimates for the risk difference and should be used for estimation purposes only.

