Immune-related adverse events (irAEs): in the pooled safety data (N=1738), a total of 247 patients (14.2%) experienced irAEs, defined as adverse events requiring use of corticosteroids (and/or hormonal therapy for endocrinopathies), and no clear alternate etiology. The median time to first onset of an irAE was 11.7 weeks. The most frequent irAEs were thyroid disorders including hypothyroidism (5.2%), hyperthyroidism (0.4%) and thyroiditis (0.2%), immune-related rash (5.2%), immune-related colitis (1.5%), immune-related pneumonitis (1.2%), immune-related hepatitis (0.9%), adrenal insufficiency (0.5%) and immune-related myositis (0.5%). In addition, irAEs reported in 0.1% of patients in the pooled safety dataset included: type 1 diabetes mellitus, immune-related nephritis/renal dysfunction, hypopituitarism, uveitis and Guillain-Barre Syndrome. The majority of irAEs were Grade 1 or Grade 2 in severity, with 39 (2.2%) being of Grade  $\geq 3$  severity. Fatal outcome was reported in 1 patient (0.1%) with immune-related pneumonitis, and 2 patients (0.1%) with immune-related hepatitis. Other relevant irAEs reported with avelumab outside

the pooled safety dataset included 1 case of fatal immune-related myocarditis in Study B9991002 (avelumab in combination with axitinib for renal cell carcinoma (RCC)), 1 case of non-fatal immune-related myocarditis in the 20 mg/kg cohort of the dose escalation phase of Study EMR100070-001, and 2 patients with non-fatal graft versus host disease (GVHD) in Study B9991007 (avelumab in patients with classical Hodgkin's lymphoma).

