## 2.2. Study Design

This is a Phase 3, international, multicenter, randomized, double-blind, parallel, 2-arm study in patients with previously untreated, histologically confirmed locally advanced SCCHN (oral cavity, oropharynx, larynx, or hypopharynx) who are candidates for definitive chemoradiotherapy (CRT) with cisplatin.

A total of approximately 640 patients will be randomized in a 1:1 ratio to either Arm A (avelumab + SOC CRT) or Arm B (placebo + SOC CRT). Randomization will be stratified by tumor (T) stage (<T4 vs T4), nodal (N) stage (N0/N1/N2a/N2b vs N2c/N3), and HPV status (positive vs negative) as measured by p16 expression by immunohistochemistry (IHC).

The study schematic is provided in Figure 1.

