##### 4.2. Safety Analysis Set

The safety analysis set will include all patients who receive at least one dose of study drug. Patients will be classified according to the study treatment assigned at randomization unless the incorrect treatment(s) was/were received throughout the dosing period in which case patients will be classified according to the first study treatment received.

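### The exact interval named for adverse-event risk differences is very conservative for rare events if read as ordering on the raw difference; SAP 6.6.4 should specify a score-based interval

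*SAP*

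**What the plan says.** SAP 6.6.4 plans, by preferred term or clustered term, "Point estimate for risk difference and 95% CI for risk difference (experimental arm vs comparator arm") for immune-related adverse events (irAEs), avelumab-associated infusion-related reactions (IRRs) and Tier-2 events, each at any grade and at Grade 3 or higher. On method it says only that "CIs for risk difference will be calculated based on the unconditional exact method by Santner and Snell". Neither the section nor the reference list names the ordering statistic or a software option.

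On purpose, the section says the intervals are unadjusted for multiplicity and meant for screening, and that "The 95% CIs are provided to help gauge the precision of the estimates for the risk difference". No p-value or decision rule is attached to them.

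Under SAP 3.5.1 a preferred term becomes Tier-2 if it reaches 10% of patients at any grade, or 5% at Grade 3 to 5, in either arm.

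**The concern.** An unconditional exact interval takes the worst case over the unknown common event rate. If tables are ordered by the raw difference in proportions, that worst case lies near a 50% rate, where the difference is most variable, even when the observed events are rare. The interval then shows the precision expected of a 50% event rate.

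This matters because many of the events the section targets are rare. In the single-agent avelumab pool in Protocol 1.2.2, "a total of 247 patients (14.2%) experienced irAEs", "with 39 (2.2%) being of Grade" 3 or higher, and most individual irAE types were at 1.5% or below, with rash and hypothyroidism each at 5.2%. These are toxicities avelumab might be expected to add to chemoradiotherapy, and this interval is the only inferential summary the section attaches to them.

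**Working it through.** **Inputs.**
- Arm size: "A total of approximately 640 patients will be randomized in a 1:1 ratio to either Arm A" or Arm B (SAP 2.2), so 640 / 2 = 320. SAP 4.2 defines the safety set: "The safety analysis set will include all patients who receive at least one dose of study drug". I assume nearly all are dosed, so n = 320 per arm.
- Level: 95% two-sided, 0.025 per tail (SAP 6.6.4).
- Arm A rates, Protocol 1.2.2: Grade 3 or higher irAE 2.2% (0.022 × 320 ≈ 7 patients); any-grade irAE 14.2% (≈ 45); rash 5.2% (≈ 17); pneumonitis 1.2% (≈ 4).
- Common Grade 3-4 chemoradiotherapy toxicities, Protocol 1.3: mucositis 33% (≈ 106), dysphagia 57% (≈ 182).
- Tier-2 Grade 3 or higher threshold: 5% (0.05 × 320 = 16).
- Comparator rates: not given in the documents, so varied from 0 up to equality with Arm A.

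The plan states no expected interval width, so there is no figure of its own to reproduce.

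**Method.** Two one-sided exact tests at 0.025 were inverted, with the tail probability maximised over the nuisance rate on a grid. This was done (a) ordering on the raw difference x1/n - x2/n, and (b) ordering on the score statistic, which standardises the difference using the rates estimated under the hypothesised difference. Both are unconditional exact intervals.

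**Analytic check of (a).** The worst-case width is about 2 × 1.96 × √(2 × 0.25 / 320) = 3.92 × 0.0395 = 15.5 points. The exact computation gives 15.8, or -7.9 to 7.9 when the arms are equal.

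**Results (percentage points).**

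| Patients, A vs B | (a) Raw difference | Width | (b) Exact score | Width | Ratio of widths |
|---|---|---|---|---|---|
| 4 vs 0 | -6.6 to 9.1 | 15.8 | 0.0 to 3.2 | 3.2 | 4.9 |
| 7 vs 0 | -5.7 to 10.1 | 15.8 | 0.7 to 4.5 | 3.7 | 4.3 |
| 7 vs 7 | -7.9 to 7.9 | 15.8 | -2.6 to 2.6 | 5.2 | 3.0 |
| 16 vs 0 | -2.9 to 12.9 | 15.8 | 2.9 to 8.0 | 5.1 | 3.1 |
| 16 vs 16 | -7.9 to 7.9 | 15.8 | -3.6 to 3.6 | 7.1 | 2.2 |
| 17 vs 3 | -3.5 to 12.2 | 15.8 | 1.5 to 7.6 | 6.1 | 2.6 |
| 45 vs 6 | 4.3 to 20.0 | 15.7 | 8.2 to 16.6 | 8.4 | 1.87 |
| 45 vs 16 | 1.2 to 16.9 | 15.7 | 4.4 to 13.8 | 9.5 | 1.65 |
| 45 vs 45 | -7.9 to 7.9 | 15.8 | -5.5 to 5.5 | 10.9 | 1.45 |
| 106 vs 106 | -7.9 to 7.9 | 15.8 | -7.3 to 7.3 | 14.7 | 1.07 |

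At 182 vs 182 (57%), (a) is 15.8 wide and a Newcombe interval is 15.3, a ratio of 1.03.

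**Excluding zero under (a).** At a hypothesised difference of zero, the maximised one-sided tail is 0.0263 for a 25-patient difference and 0.0219 for 26. The lower limit therefore exceeds zero only from 26 / 320 = 8.1 points upward, however rare the event. A Grade 3 or higher term that just reaches Tier-2 (16 patients) cannot exclude zero even with no placebo cases, although Fisher's two-sided p for 16 vs 0 is 2.5 × 10⁻⁵. At 24 vs 0 the interval is still -0.4 to 15.3.

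**How conservative (a) is.** With both true rates at 2.2%, the chance of a difference of 26 or more in favour of Arm B is about 8 × 10⁻¹¹, against a nominal 0.025. With true rates of 5% and 1%, the lower limit would exceed zero with probability about 0.0025.

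**The case against.** The strongest reply is that the SAP never says the raw difference is the ordering statistic. Under score ordering, also an unconditional exact method, widths at the irAE rates tested are 3.2 to 10.9 points and the problem disappears. That stands as a limit on the claim: the 15.8-point figure is conditional. It does not remove the point. The text names the method with no score modification, and the two readings differ about fourfold for 7 vs 0, so the SAP needs to settle the choice.

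Second, a reader might infer that the plan hides real harm. The documents do not support that. SAP 6.6.4 gives the point estimate beside each interval and tabulates irAEs by arm, cluster and preferred term, including Grade 3 or higher, serious and fatal events. SAP 3.5.1 treats safety analyses as exploratory, and Protocol 9.7 has the external data monitoring committee review unblinded safety data every 6 months. Anyone shown 16 vs 0 sees the imbalance.

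Third, a reader might take the 2-to-4-fold excess to cover all irAEs and all Grade 3 or higher events. It does not: the table shows ratios of 1.45 to 1.87 for any-grade irAEs at 14.2%, and 45 vs 16 excludes zero under either ordering. Common chemoradiotherapy toxicities hardly change.

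Fourth, the comparator rates are assumed, and the irAE rates come from avelumab alone. Protocol 5.5.2.4 lists hypothyroidism as a late radiation effect, so near-zero control rates are not assured for every cluster. This is why the table runs up to equal rates, where the excess width remains for events at 5% or below.

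**Conclusion.** The point holds for rare events and on a stated assumption. With raw-difference ordering and about 320 treated per arm, the interval is about 15.8 points wide at almost any rate. For events at about 5% or below (Grade 3 or higher irAEs, most individual irAE clusters and terms, Grade 3 or higher Tier-2 events near the 5% threshold), this is about 2 to 4 times the exact score width, and more below 2%. Zero stays inside the interval until the arms differ by 26 patients.

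The interval is conservative, not invalid: its coverage is guaranteed. The cost is that it misstates precision and screens poorly for rare events, which are the two uses the SAP gives it. The primary endpoint, type I error control and stopping rules are untouched. Severity is minor to moderate.

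**What to change.** In SAP 6.6.4, state that for all Tier-1 and Tier-2 risk differences the limits are exact unconditional limits based on the standardised score statistic. This keeps the guaranteed coverage of an exact method. Miettinen-Nurminen limits are an acceptable alternative, but their coverage is only approximate.

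The cost is one sentence in the SAP and one software option, with no new data and no change to any other analysis. If the sponsor already intends score ordering, the same sentence settles the ambiguity.

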### **6.6.5. Laboratory data**

#### **6.6.5.1. Hematology and chemistry parameters**

Laboratory results will be classified according to the NCI-CTCAE criteria version 4.03. Non-numerical qualifiers (with the exception of fasting flags) will not be taken into consideration in the derivation of CTCAE criteria (eg, hypokalemia Grade 1 and Grade 2 are only distinguished by a non-numerical qualifier and therefore Grade 2 will not be derived). Additional laboratory results that are not part of NCI-CTCAE will be presented according to the categories: below normal limit, within normal limits and above normal limit (according to the laboratory normal ranges).

Quantitative data will be summarized using simple descriptive statistics (mean, SD, median, Q1, Q3, minimum, and maximum) of actual values and changes from baseline for each nominal visit over time (unscheduled measurements would therefore not be included in these summaries as described in Section 5.2.9). End of Treatment visit laboratory results will be summarized separately. The changes computed will be the differences from baseline. Qualitative data based on reference ranges will be described according to the categories (ie, Low, Normal, High).

Abnormalities classified according to NCI-CTCAE toxicity grading version 4.03 will be described using the worst grade. For those parameters which are graded with two toxicities such as potassium (hypokalemia/hyperkalemia), the toxicities will be summarized separately. Low direction toxicity (eg, hypokalemia) grades at baseline and post baseline will be set to 0 when the variables are derived for summarizing high direction toxicity (eg, hyperkalemia), and vice versa.

For **WBC differential counts** (total neutrophil [including bands], lymphocyte, monocyte, eosinophil, and basophil counts), the absolute value will be used when reported. When only percentages are available (this is mainly important for neutrophils and lymphocytes, because the CTCAE grading is based on the absolute counts), the absolute value is derived as follows:

$$\text{Derived differential absolute count} = (\text{WBC count}) \times (\text{Differential \%value} / 100)$$

If the range for the differential absolute count is not available (only range for value in % is available) then Grade 1 will be attributed to as follows:

- Lymphocyte count decreased:
  - derived absolute count does not meet Grade 2-4 criteria, and
  - % value < % LLN value, and
  - derived absolute count  $\geq 800/\text{mm}^3$
- Neutrophil count decreased
  - derived absolute count does not meet Grade 2-4 criteria, and
  - % value < % LLN value, and
  - derived absolute count  $\geq 1500/\text{mm}^3$

For **calcium**, CTCAE grading is based on Corrected Calcium and Ionized Calcium (CALCIO). Corrected Calcium is calculated from Albumin and Calcium as follows

$$\text{Corrected calcium (mmol/L)} = \text{measured total Calcium (mmol/L)} + 0.02 (40 - \text{serum albumin [g/L]})$$

**Liver function tests:** Alanine aminotransferase (ALT), aspartate aminotransferase (AST), and total bilirubin (TBILI) are used to assess possible drug induced liver toxicity. The ratios of test result over upper limit of normal (ULN) will be calculated and classified for these three parameters during the on-treatment period.

Summary of liver function tests will include the following categories. The number and percentage of patients with each of the following during the on-treatment period will be summarized by treatment arm:

- ALT  $\geq 3 \times \text{ULN}$ , ALT  $\geq 5 \times \text{ULN}$ , ALT  $\geq 10 \times \text{ULN}$ , ALT  $\geq 20 \times \text{ULN}$ ;
- AST  $\geq 3 \times \text{ULN}$ , AST  $\geq 5 \times \text{ULN}$ , AST  $\geq 10 \times \text{ULN}$ , AST  $\geq 20 \times \text{ULN}$ ;

- (ALT or AST)  $\geq 3 \times \text{ULN}$ , (ALT or AST)  $\geq 5 \times \text{ULN}$ , (ALT or AST)  $\geq 10 \times \text{ULN}$ , (ALT or AST)  $\geq 20 \times \text{ULN}$ ;
- TBILI  $\geq 2 \times \text{ULN}$ ;
- Concurrent ALT  $\geq 3 \times \text{ULN}$  and TBILI  $\geq 2 \times \text{ULN}$ ;
- Concurrent AST  $\geq 3 \times \text{ULN}$  and TBILI  $\geq 2 \times \text{ULN}$ ;
- Concurrent (ALT or AST)  $\geq 3 \times \text{ULN}$  and TBILI  $\geq 2 \times \text{ULN}$ ;
- Concurrent (ALT or AST)  $\geq 3 \times \text{ULN}$  and TBILI  $\geq 2 \times \text{ULN}$  and ALP  $> 2 \times \text{ULN}$ ;
- Concurrent (ALT or AST)  $\geq 3 \times \text{ULN}$  and TBILI  $\geq 2 \times \text{ULN}$  and (ALP  $\leq 2 \times \text{ULN}$  or missing).

Concurrent measurements are those occurring on the same date.

Categories will be cumulative, ie, a patient with an elevation of AST  $\geq 10 \times \text{ULN}$  will also appear in the categories  $\geq 5 \times \text{ULN}$  and  $\geq 3 \times \text{ULN}$ . Liver function elevation and possible Hy's Law cases will be summarized using frequency counts and percentages.

An evaluation of Drug-Induced Serious Hepatotoxicity (eDISH) plot will also be created, with different symbols for different treatment arms, by graphically displaying

- peak serum ALT(/ULN) vs peak total bilirubin (/ULN) including reference lines at ALT=3 $\times$ ULN and total bilirubin=2 $\times$ ULN;
- peak serum AST(/ULN) vs peak total bilirubin (/ULN) including reference lines at AST=3 $\times$ ULN and total bilirubin=2 $\times$ ULN.

In addition, a listing of all TBILI, ALT, AST and ALP values for patients with concurrent (ALT or AST)  $\geq 3 \times \text{ULN}$  and TBILI  $\geq 2 \times \text{ULN}$  and (ALP  $\leq 2 \times \text{ULN}$  or missing) will be provided.

